6.3 Clinical Response

Clinical response will be measured by reduction of WOMAC pain score on the Study Knee. In order for a subject to be considered to have successfully obtained a clinical response, the following criteria must be met: WOMAC pain score on the Study Knee reduced to 50% or less of baseline at any of the stated assessment times.

A subject with a missing WOMAC pain score on the Study Knee at a visit will be considered to have failed to achieve a clinical response for that visit.

The durability of clinical response up to Day 94 will be evaluated by a tabulation of clinical response at Days 19, 35, 64, and the Day 94 visit by treatment group. Subjects who have successfully met the above criteria (reduction of a least 50% in WOMAC pain score) at the Day 5 visit and who remain at least at this reduction of pain score or lower at the Days 19, 35, 64, and the Day 94 visit will be considered to have a durable clinical response through Day 94. Subjects who at no more than one of the post Day 5 visits have less than 50% reduction in WOMAC pain score will be considered to have a durable response through the last day at which reduction in WOMAC pain score is at least 50%. Patients who have less than 50% WOMAC pain score reduction on two or more of the post Day 5 visits will be considered to have failed to achieve a durable clinical response.

Each subject's clinical response status (Responder vs. Non-responder) at each visit and the durability of clinical response up to Day 94 will be summarized for each treatment group. Percent change from baseline in WOMAC pain score on both knees will be listed at each visit.

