9.5.3.1 Clinical Response

Clinical response will be measured by reduction of WOMAC pain score. In order for a subject to be considered to have successfully obtained a clinical response, the following criteria must be met:

WOMAC pain score reduced to 50% or less of baseline at any of the stated assessment times.

The durability of clinical response up to Day 94 will be evaluated by a tabulation of clinical response at a Days 19, 35, 64, and the Day 94 visit by treatment group. Subjects who have successfully met the above criteria (reduction of a least 50% in NRS pain score) at the Day 5 visit and who remain at least at this reduction of pain score or lower at the Day 35 visit will be considered to have a durable clinical response. Subjects who at the Day 35 visit have less reduction in WOMAC in OAKP score than they did at the Day 5 assessment will be considered to have failed to achieve a durable clinical response.

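### SAP 6.3 counts post-Day-5 lapses without a Day 5 condition, so some Day 5 non-responders are labelled durable responders (minor wording error in a descriptive classification)

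*SAP*

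**What the plan says.** SAP 6.3 defines response at a visit as "WOMAC pain score on the Study Knee reduced to 50% or less of baseline at any of the stated assessment times". A missing score counts as non-response: "A subject with a missing WOMAC pain score on the Study Knee at a visit will be considered to have failed" at that visit.

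Three sentences then classify durability.

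- **Rule A.** Subjects who respond "at the Day 5 visit and who remain at least at this reduction of pain score or lower" at Days 19, 35, 64 and 94 are durable through Day 94.
- **Rule B.** This applies to "Subjects who at no more than one of the post Day 5 visits have less than 50% reduction in WOMAC pain score". Its label, with no mention of Day 5, is that they "will be considered to have a durable response through the last day at which reduction in WOMAC pain score is at least 50" percent.
- **Rule C.** "Patients who have less than 50% WOMAC pain score reduction on two or more of the post Day 5 visits" are failures.

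Protocol 9.5.3.1 ties both of its rules to Day 5. Durable subjects respond "at the Day 5 visit and who remain at least at this reduction of pain score or lower at the Day 35 visit". Failures "have less reduction in WOMAC in OAKP score than they did at the Day 5 assessment".

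SAP 6.3 summarises durability by treatment group and specifies no test.

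**The concern.** Rule A and the protocol treat durability as an early response that lasts. Rules B and C drop the early response and count only lapses after Day 5. Because 'at most one' and 'two or more' cover every possibility, B and C alone classify every subject, and Day 5 status never changes the result. A subject with no response at Day 5 or Day 19 who responds at Days 35, 64 and 94 is durable through Day 94.

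At stake is what the durable-response count means. As written it mixes response present 24 hours after the last application and then kept with response first reached two weeks or more later. A programmer has to choose a reading, and the choice changes the counts by arm. Protocol 1.1 presents long-lasting relief after a brief course as the unmet need, so these counts are likely to be quoted.

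**Working it through.** **Inputs.** The response criterion, missing-score rule and Rules A to C are from SAP 6.3; the Day 5 and Day 35 rule is from Protocol 9.5.3.1. The documents state no durability figure, so there is none to reproduce.

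**Step 1: enumerate.** Five visits (Days 5, 19, 35, 64, 94), each response (1) or not (0), give 2^5 = 32 patterns, 16 for each Day 5 status. Among the four later visits, the patterns with at most one lapse number C(4,0) + C(4,1) = 1 + 4 = 5. The other 16 − 5 = 11 have two or more.

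| Day 5 status | Durable, B as written | Failed, C | No category if B is limited to Day 5 responders |
|---|---|---|---|
| Responder (16) | 5 | 11 | 0 |
| Non-responder (16) | 5 | 11 | 5 |
| All (32) | 10 | 22 | 5 |

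**Step 2: the five patterns.** All have Day 5 = 0.

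| Days 19, 35, 64, 94 | Label under B as written | Rule A | Protocol 9.5.3.1 |
|---|---|---|---|
| 1, 1, 1, 1 | durable through Day 94 | not met | not durable |
| 0, 1, 1, 1 | durable through Day 94 | not met | not durable |
| 1, 0, 1, 1 | durable through Day 94 | not met | not durable |
| 1, 1, 0, 1 | durable through Day 94 | not met | not durable |
| 1, 1, 1, 0 | durable through Day 64 | not met | not durable |

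A subject with no Day 5 score has Day 5 = 0 under the missing-score rule and is handled the same way.

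**Step 3: illustrate the size.** The rates are assumptions. Let p5 be the Day 5 response rate, pL the rate at each later visit, and ρ a latent-normal within-subject correlation. Given a standard normal subject effect z,

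- a = Φ[(Φ⁻¹(p5) − √ρ·z)/√(1−ρ)], and b is the same with pL in place of p5;
- durable as written: D = E[b⁴ + 4b³(1−b)];
- Day 5 non-responders among them: N = E[(1−a)(b⁴ + 4b³(1−b))];
- durable with the Day 5 condition: D − N; share affected: N/D.

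| p5 / pL / ρ | D | D − N | N/D | 40 × N (per arm) |
|---|---|---|---|---|
| 90% / 70% / 0.5 | 65% | 63% | 3% | 0.8 |
| 50% / 40% / 0.6 | 31% | 26% | 16% | 1.9 |
| 40% / 50% / 0.6 | 41% | 28% | 32% | 5.2 |
| 25% / 35% / 0.5 | 24% | 13% | 45% | 4.2 |
| 30% / 60% / 0.4 | 51% | 23% | 56% | 11.5 |

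With one common rate of 30% to 70% at all five visits and ρ of 0.5 to 0.7, N is about 5% to 11% of subjects (2 to 4 of 40 per arm) and N/D is 12% to 34%.

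**The case against.** The strongest reply is that the paragraph should be read in sequence. Rule A sets Day 5 response as the entry condition, Rule B relaxes it for a single later lapse, and anyone who never entered is plainly not durable. That may well be the intent. But B does not say so, and on that reading the five patterns meet none of the three rules. The gap closes only by a default that the SAP does not state.

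The protocol is also an imperfect benchmark. It looks only at Days 5 and 35, mixes NRS with WOMAC in its durability wording, and itself leaves unclassified a Day 5 non-responder who improves by Day 35. The SAP's revision table records that the durability definition was updated, so a difference from the protocol is not in itself an error. What stands is that Rule A and the protocol agree on the Day 5 condition while Rule B omits it.

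Counting late response could be a reasonable choice. The SAP would then have to say so and drop the Day 5 condition from Rule A.

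A reader might also infer more than the documents support:

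- **That the trial loses its evidence of lasting benefit.** It does not. SAP 6.2 and 6.3 also give response status by visit and WOMAC summaries to Day 94.
- **That an efficacy endpoint is broken.** Durability is not among the primary or secondary efficacy endpoints in SAP 2.2, and it is untested.
- **That all Day 5 non-responders are left unclassified.** Eleven of their 16 patterns fail under Rule C on either reading.
- **That one arm is favoured.** Protocol 1.1 and 1.3 report response 24 hours after the fourth application of 25% for once-daily vehicle in VZU00022 and 100% for CGS-200-05 in VZU00021. These used different scales in different countries, and vehicle did about as well as active in VZU00023. They show that equal effects across arms cannot be assumed, but they do not give a direction.

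**Conclusion.** Wrong as written, and minor. Rules B and C label 5 of 16 Day 5 non-responder patterns durable, against the Day 5 condition in Rule A and the protocol; the alternative reading leaves the same 5 without a category. This follows from the wording alone.

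The practical size is not known. The settings tried put Day 5 non-responders at about 3% to 56% of subjects labelled durable. The low end needs a very high Day 5 rate (90%), and the high end needs a rise from 30% at Day 5 to 60% at every later visit. These are illustrations, not bounds or forecasts.

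The effect is confined to the descriptive durability counts by arm. The primary ANCOVA in SAP 6.1, the power in SAP 9 and the by-visit response and WOMAC summaries do not use this classification.

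**What to change.** Before unblinding, make two changes in SAP 6.3.

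1. Begin the second classifying sentence with: *Among subjects with at least 50% reduction at Day 5*.
2. Add: *Subjects without at least 50% reduction at Day 5, including those with a missing Day 5 score, are not durable responders.*

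Every pattern then has exactly one durability status, and the durable patterns fall from 10 to 5 of 32. A separate row for late response is optional, because response by visit is already tabulated.

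The cost is a clause, a sentence and a small programming change. The reported durable-response rate will be somewhat lower. Make the change in the same redraft as any other correction to this paragraph, since a reading chosen after unblinding could look driven by the results.

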6.4 Exploratory Analyses

Post hoc tests may be performed to test for differences in the efficacy endpoints between the CGS-200-0 (Vehicle), CGS 200-1 and CGS-200-5 treatment groups for exploratory purposes.

6.5 Tolerability Analyses

The primary tolerability endpoint will be tolerability of the formulations on each of Days 1, 2, 3, and 4. On each of these days, subjects will report an NRS score for burning / stinging at the application site pre-treatment and during treatment, and a pre-treatment and during treatment pruritus score. Pre-treatment and during treatment erythema and scaling scores will be recorded by clinic staff assigned to the study. This will be done at 0, 15, 30, 60, and 90 minutes after application to capture time points during treatment and after washing the application site. The score for each of the above tolerability variables will be entered as a value at each assessment time.

For each subject, an area under the curve (AUC) calculation will be performed in 90 minute intervals for each score value. The AUC for a specified time interval will be calculated using the

trapezoidal rule. If we have $n+1$ measurements y_i at times t_i ($i=0, 1, \dots, n$), then the AUC is calculated as $AUC = \frac{1}{2} \sum_{i=0}^{n-1} (t_{i+1} - t_i)(y_i + y_{i+1})$.

For each of Days 1 through 4, the average of AUC from left and right knees will be calculated for each of the tolerability variables. The calculated average of AUC from all the tolerability variables will then be combined and compared between each Active Treatment Arm (CGS-200-5 and CGS-200-1) and the Vehicle Arm (CGS-200-0) using analysis of variance (ANOVA).

A listing will be provided for all the tolerability variables at each visit.

7. SAFETY ANALYSIS

Safety assessments will include assessment of DLT, AEs, chemistry, hematology (complete blood count and differential), coagulation profile, urinalysis, and vital signs. All safety summaries (or analyses if applicable) will be conducted using the SAF set. No formal hypothesis testing will be performed to compare differences between treatment groups.

7.1 Extent of Exposure

The estimated percentage of study drug applied to each knee, the reason for full dose not being applied, and the duration of study drug application on each knee at each visit will be summarized for each treatment group.

7.2 Adverse Events

The AE monitoring period begins with the start of study drug administration on Day 1 and continues through Day 94.

An AE is any unfavorable or unintended sign, symptom, or disease that is temporally associated with the use of an investigational drug, but it is not necessarily caused by the investigational drug. This includes worsening (e.g., increase in frequency or severity) of pre-existing conditions. AEs will be classified by SOC and PT using the most recent version of Medical Dictionary for Regulatory Activities (MedDRA).

7.2.1 Treatment-emergent Adverse Events

A treatment-emergent AE (TEAE) is defined as an event that first occurs or worsens in intensity after the administration of study drug.

7.2.2 Adverse Event Severity

Severity will be graded using the Rheumatology Common Toxicity Criteria (RCTC), v2.0². The RCTC is provided in Appendix B of the protocol. In the event that an AE does not have a RCTC code, the following severity classifications will be used:

- Grade 1-Mild: Causing no limitation of usual activities
- Grade 2-Moderate: Causing some limitation of usual activities
- Grade 3-Severe: Causing inability to carry out usual activities
- Grade 4-Life Threatening: Potentially life threatening or disabling

7.2.3 Adverse Event Relationship to Study Medication

The investigator is required to provide an assessment of causality or relationship of AEs to the study drug based on 1) temporal relationship of the event to the administration of study drug; 2) whether an alternative etiology has been identified; and 3) biological plausibility. The causality assessment categories that will be used for this study are “Not Related” (referring to “None” or “Unlikely”), and “Related” (referring to “Possible”, “Probable”, or “Definite”). See the study protocol, Section 8.1.3.3 for full details.

7.2.4 Serious Adverse Events

A serious adverse event (SAE) is an AE resulting in any of the following outcomes:

- Death
- Life-threatening (**immediate** risk of death)
- Inpatient hospitalization
- Prolongation of existing hospitalization
- Persistent or significant disability or incapacity
- Congenital anomaly/birth defect
- Medically important

7.2.5 Adverse Event Summaries

All AEs (serious and non-serious) occurring after study drug administration and before the end of study, regardless of relationship to study drug, will be included and classified by SOC and PT using MedDRA.

For TEAEs, the following will be summarized and presented for the SAF set:

- i. An overall summary of TEAEs, which includes:
 - a. the number and percentage of subjects experiencing a TEAE
 - b. the number and percentage of subjects experiencing a TEAE by strongest relationship to study medication
 - c. the number and percentage of subjects experiencing a TEAE by highest RCTC toxicity grade
 - d. the number and percentage of subjects experiencing a DLT
 - e. the number and percentage of subjects experiencing a treatment emergent SAE (TESAE)
 - f. the number and percentage of subjects experiencing a TEAE leading to death
 - g. the number and percentage of subjects experiencing a TEAE leading to study withdrawal
 - ii. the number and percentage of subjects experiencing a TEAE by SOC and PT.
 - iii. the number and percentage of subjects experiencing a TEAE by SOC, PT and the strongest
-

relationship to study medication

- iv. the number and percentage of subjects experiencing a TEAE by SOC, PT and the highest RCTC toxicity grade
- v. the number and percentage of subjects experiencing a DLT by SOC and PT
- vi. the number and percentage of subjects experiencing a TESAE by SOC and PT
- vii. the number and percentage of subjects experiencing a TEAE leading to study withdrawal by SOC and PT

In the overall summary of TEAEs table (i), besides tabulating the number and percentage of subjects, the total number of TEAE episodes will also be provided. If a subject has repeated episodes of a particular TEAE, all episodes will be counted in the summary table.

In the remaining summary tables, the incidence of TEAEs will be calculated by dividing the number of subjects who have experienced the event by the total number of subjects in the SAF set. Thus, the incidence of TEAEs is shown in terms of the total number of subjects and not in terms of the total number of episodes. If a subject has repeated episodes of a particular TEAE, only the most severe episode, or the episode with the strongest causal relationship to study drug, will be counted in the summary tables.

A subject with more than one type of TEAE in a particular SOC will be counted only once in the total of subjects experiencing TEAEs in that particular SOC. Since a subject could have more than one type of TEAE within a particular SOC, the sum of subjects experiencing different TEAEs within the SOC could appear larger than the total number of subjects experiencing TEAEs in that SOC. Similarly, a subject who has experienced a TEAE in more than one SOC will be counted only once in the total number of subjects experiencing AEs in all SOCs.

All occurrences of all AEs and SAEs will be listed for each subject, grouped by treatment group. The listing will contain the following information: treatment group, verbatim term, SOC, PT, toxicity grade, relationship to study medication, date and day of onset, date and day of resolution, treatment given to treat the adverse event, the outcome, whether the event was an SAE, whether it led to study withdrawal, whether the event was a DLT, and whether it is a TEAE. Listings will be sorted by treatment group, subject identification number, onset date, SOC, and PT. If the onset date is completely missing, then these events will be presented first. If the onset date is missing a month or a day, then these events will be presented before any complete dates.

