5.1.4 Dosage and Administration

The study medication is for external use only and will be administered at the clinic by the subject under the supervision of trained site personnel. Wearing gloves, supplied by the clinic staff, a single dose of the assigned treatment will be topically applied to each knee on each of four dosing days. Both knees will be treated for all subjects, if possible, however only one knee will be the study knee on which assessments are performed. The first application of medication will be at Visit 2 on Day 1 (initiated at Time 0). Dosing on each of the three subsequent treatment days should be performed at the same time of day ± 2 hours in relation to the start time of the initial dose on Day 1.

With the knee relaxed, in a straight and horizontal position, treatment will begin by identifying a 10 cm by 10 cm area where the upper boundary is 1 cm above the patella, the center is aligned with the midline of the patella, and the line bisecting the 10 cm by 10 cm square has 5 cm on either side medially and laterally to the midline of the patella. Each application of the study medication will consist of a single pass of the roller ball over the knee so as to completely cover the designated treatment area. The treatment will be applied continuously beginning at the upper left corner of the square and moving the rollerball horizontally to the upper right corner and moving back and forth in a continuous pattern in a downward progression until the entire square is covered. This should result in moistening the skin providing a thin film of medication (approximately 0.13 mL [or 0.13 gram] of drug product applied to 100 cm² of knee surface, which represents 1.3 mg of solution per cm²). Areas that were already moistened should not be recoated. The study medication should not be applied to a knee if the subject is still experiencing stinging, burning, pruritus, erythema, or scaling from a prior application to that knee. In the case of a dose that is skipped, the subject should return as scheduled for their next visit at which time they may receive the next scheduled application of study medication if their symptoms have subsided. The treatment period will not be extended beyond 4 days.

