6.10 WITHDRAWAL OF SUBJECTS FROM STUDY

Subjects will be free to withdraw from treatment or from the study at any time for any reason, or they may be withdrawn/removed, if necessary (see reasons for withdrawal below). It is understood by all concerned that an excessive rate of withdrawals can render the study uninterpretable; therefore, unnecessary withdrawal of subjects should be avoided.

Subjects will be removed from treatment for the following reasons:

- Unacceptable acute toxicities defined as:
 - Occurrence of a DLT

Subjects will be removed from the study for the following reasons:

- Withdrawal of consent
- Non-compliance/Lost to follow-up
- Pregnancy

If treatment with study drug is interrupted and permanently stopped, subjects should remain on study and will be followed for scheduled safety and study assessments through Day 35. If the subject goes onto other treatment, this should be noted in the source documents and the concomitant medications eCRF.

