9.5.5 Safety Analyses

9.5.5.1 Adverse Events

The incidence of all reported AEs and treatment-emergent AEs (TEAE) will be tabulated. A TEAE is defined as an event that first occurs or worsens in intensity after the administration of study drug. AEs will be classified by system organ class and preferred term using the Medical Dictionary for Regulatory Activities (MedDRA). The severity of the AE will be graded using the RCTC v2.0 whenever possible. For AEs that are not included in the RCTC v2.0, the grading categories (mild, moderate, severe, and life-threatening) will be used and equated to the respective RCTC grade (Grades 1, 2, 3, and 4). For incidence reporting, if a subject reports more than one AE that is coded to the same system organ class or preferred term, the subject will be counted only once for that specific system organ class or preferred term.

An overview of AEs, which includes subject incidence of TEAEs, treatment-related AEs, severity of AEs, SAEs, deaths, and AEs leading to discontinuation, will be presented. For AEs presented by severity, the worst severity during the study will be presented for each subject. The subject incidence of TEAEs will be summarized by system organ class and preferred term. The subject incidence of treatment-related AEs and RCTC v2.0 toxicity grade will be summarized by preferred term.

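### SAP 7.2.5 counts adverse events that end study participation but not those that end dosing, although the protocol keeps subjects who stop drug in follow-up

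*SAP*

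**What the plan says.** Protocol 9.5.5.1 describes an adverse event overview in which "SAEs, deaths, and AEs leading to discontinuation, will be presented". It does not say whether discontinuation means of drug or of study.

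The SAP settles on the study. Section 7.2.5 has an overview item (i.g) giving "the number and percentage of subjects experiencing a TEAE leading to study withdrawal", and a table (vii) giving the same count by system organ class and preferred term. The adverse event listing carries the flags "whether it led to study withdrawal, whether the event was a DLT, and whether it is a TEAE". No item in 7.2.5 records that an event stopped, interrupted or prevented an application.

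The protocol separates the two outcomes. Section 6.10 gives a DLT as the only listed reason for removal from treatment. A second list, opening "Subjects will be removed from the study for the following reasons", contains consent withdrawal, non-compliance or loss to follow-up, and pregnancy; an adverse event is not on it. The section then says "If treatment with study drug is interrupted and permanently stopped, subjects should remain on study", with assessments through Day 35. SAP 3.2.4 repeats all of this.

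Doses can also be lost without a permanent stop. Under Protocol 5.1.4 drug is not applied to a knee still reacting to a prior application, and "In the case of a dose that is skipped, the subject should return as scheduled for their next visit". The course is not extended beyond four days.

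**The concern.** In many trials stopping drug and leaving the study nearly coincide, and one table serves for both. Here the protocol deliberately separates them. A subject who stops on Day 2 because of burning and then attends follow-up has an adverse event that ended treatment, yet is not a study withdrawal. If the sponsor meant the SAP table to deliver what Protocol 9.5.5.1 describes, it counts a different event.

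The stake is a stated objective: to confirm in a U.S. population the safety profile of CGS-200-5 seen in the two Dominican Republic studies. Protocol 1.3 describes that profile partly as an absence of adverse events causing discontinuation or subject-requested withdrawal, naming the two side by side. The U.S. report would have an adverse event table for one of them only. A low or zero count there could be taken to mean that reactions did not end treatment, which the table cannot show.

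**Working it through.** No figure in the plan is at issue, so the check is textual. For each way an adverse event can cost a subject doses or participation, I looked for the SAP output that counts it and asked whether that output ties the consequence to the event term.

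| Route | Protocol source | SAP output | Consequence tied to the event? |
|---|---|---|---|
| Event meets a DLT criterion; drug stopped | 3.2, 6.9.2, 6.10 | 7.2.5 i.d, table v, listing flag | Yes, through DLT status |
| Related event of Grade 3 or higher during application; drug stopped | 6.9.3 | Same DLT outputs, since such an event also falls under 3.2 with its threshold at Grade 3 | Yes |
| Application-site reaction below Grade 3; subject chooses to stop drug and stays in follow-up | 3.2 (site threshold), 6.10 (free to leave treatment) | General TEAE tables; medication completion in 5.1; reasons for incomplete dose in 7.1 | No |
| Application withheld or interrupted for a reaction below the DLT threshold | 5.1.4 (no grade threshold for withholding), 6.7.1 | General TEAE tables; 7.1 by knee and visit | No |
| Event leads the subject to leave the study | 6.10 (free to leave at any time) | 7.2.5 i.g, table vii, listing flag | Yes |

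The third and fourth rows are the gap. It is chiefly about application-site reactions because Protocol 3.2 sets their threshold at Grade 3, while adverse events outside its named categories count as DLTs from Grade 2. A moderate site reaction can therefore end or interrupt dosing without being a DLT.

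Other outputs come near these rows without closing them:

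- SAP 7.1 gives the reason a full dose was not applied, the percentage applied and the duration, by knee, visit and arm. It shows lost applications, but not the preferred term, grade or causality behind each, nor the number of subjects with such an event.
- SAP 5.1 separates completion of medication from completion of the study, at disposition level.
- SAP 6.5 compares a combined AUC of burning, pruritus, erythema and scaling scores. It measures intensity, not whether dosing stopped.

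On scale, each subject has four applications per knee and a skipped one is not made up, so one skipped application is 1/4 = 25% of that knee's course. The documents give no frequency for such events.

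One ambiguity affects the withdrawal table itself. Subjects who stop drug are followed through Day 35, while the schedule of events places study exit at Day 94. Neither document says whether an exit at Day 35 after a drug stop is recorded as study withdrawal. The table vii count could therefore depend on coding.

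**The case against.** The strongest reply is that little is lost. The only listed reason for removal from treatment is a DLT, and DLTs are counted overall, tabulated by term and flagged. Missed and shortened applications appear by arm in SAP 7.1, at the knee level where skipping is decided. The reactions themselves appear in the TEAE tables by grade and relationship, and in the AUC analysis. Discontinuation in Protocol 9.5.5.1 could mean study discontinuation, and that section says nothing of withheld or interrupted applications.

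Most of this stands. The events are not hidden, and a dedicated interruption table would go beyond what the protocol undertakes. What does not stand is the idea that nothing needs changing. Protocol 6.10 distinguishes treatment from study, so the SAP should say which it reports, and no listed output links a sub-DLT event to a drug stop.

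A reader might go further and infer that the withdrawal table will be near zero in every arm, or that a sizeable share of the 5% arm will stop unseen. The documents do not support either inference. Subjects may leave at any time, and the replacement rule in Protocol 4.2 allows for dropouts due to poor tolerability. Nor can the burning rates in the earlier vehicle-controlled study (100% on CGS-200-5, 35% on vehicle) stand in for stopping rates. They are incidence figures, and the same account reports grades no higher than 2 and no adverse event leading to discontinuation or withdrawal in either arm.

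**Conclusion.** The point holds in limited form. SAP 7.2.5 reports study withdrawal where Protocol 9.5.5.1 speaks of discontinuation, and in this trial the two diverge by design. What is missed at adverse event level is chiefly application-site reactions below Grade 3 that lead a subject to stop drug, or to miss an application, while remaining in follow-up.

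The number affected cannot be estimated from the documents. It may be small. The conclusion assumes that subjects who stop drug follow Protocol 6.10 and stay, and that the site records them as still in the study. If an exit at Day 35 were coded as study withdrawal, some would reach table vii, but for an administrative reason.

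The effect is confined to descriptive safety reporting; the primary efficacy analysis is untouched. The change is still worth making, because the count bears on a stated safety objective and would otherwise invite misreading.

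**What to change.** In SAP 7.2.5, at items i.g and vii and in the listing, report separately, by arm and by system organ class and preferred term:

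- TEAEs leading to permanent discontinuation of study drug;
- TEAEs leading to study withdrawal, as now planned.

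Add a listing flag for action taken with study drug, including applications withheld or interrupted. Use the AE eCRF field if there is one and add it if not; the eCRF is not among the documents. A separate table of withheld or interrupted applications by term is optional. State which meaning of discontinuation in Protocol 9.5.5.1 each table serves, and how an exit at Day 35 after a drug stop is coded.

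The cost is SAP wording, one or two more descriptive tables and possibly one eCRF field. No dosing, stopping or follow-up rule changes.
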